**Background: Participant flow and outcome measures schedule**

[figure not shown]

Figure 1 Participant flow diagram; two arm crossover design

	Baseline		During hBET use and washout period	
	Start of baseline week	Daily for baseline week	Daily	After each hBET use period (STIM and SHAM)
Pain and sleep diary		√	√	
Actigraphy		√	√	
Sleep Headband		√	√	
BPI	√			√ (weekly throughout)
PSQI	√			√
HADS	√			√
MFI	√			√
EQ5D	√			√

Table 1. Outcome measures schedule summary

## Outcome measures

### Primary Outcome measures:

#### 1. Alpha entrainment effect

Alpha spectral power during active stimulation use periods compared to sham stimulation use periods and baseline equivalent periods.

Time Frame: Baseline (1 week) vs active stimulation (2 weeks) vs sham stimulation (2 weeks)

#### 2. Sleep Quality, measured with Pittsburgh Sleep Quality Index

0-21 score of sleep quality. Within participant change, comparing active stimulation period with baseline and sham stimulation period with baseline.

Time Frame: Measured at Baseline (1 week), at completion of active stimulation, and at completion of sham stimulation (each in reference to the previous 2 weeks sleep).

### Secondary Outcome Measures:

#### 3. Sleep and Pain diary

Diary report of pain at night and over 24 hours (0-10 NRS), sleep parameters (total sleep time, sleep onset latency, wake after sleep onset, sleep efficiency) and quality (0-5 NRS) and refreshed (0-5 NRS).

Time Frame: Baseline (1 week) vs active stimulation (2 weeks) vs sham stimulation (2 weeks)

#### 4. DREEM headband derived Sleep architecture

Sleep architecture (temporal parameters, continuity, stages) as measured by Dreem 3 headband

Time Frame: Baseline (1 week) vs active stimulation (2 weeks) vs sham stimulation (2 weeks)

#### 5. Brief Pain Inventory Pain Interference score, gives a 0-10 score for pain interference.

Time Frame: Measured weekly through Baseline (1 week) active stimulation (2 weeks), washout (1 week) and sham stimulation (2 weeks).

#### 6. Actigraphy

Wrist actigraphy measures of sleep temporal parameters (total sleep time, sleep latency, wake after sleep onset, sleep efficiency).

Time Frame: Baseline (1 week) vs active stimulation (2 weeks) vs sham stimulation (2 weeks)

#### 7. Brief Pain Inventory Severity score

0-10 NRS for pain severity

Time Frame: Measured weekly through Baseline (1 week) active stimulation (2 weeks), washout (1 week) and sham stimulation (2 weeks)

#### 8. Hospital Anxiety and Depression Scale

Scores of 0-21 for anxiety, 0-21 for depression

Time Frame: Measured at Baseline (1 week), at completion of active stimulation, and at completion of sham stimulation

#### 9. Multidimensional Fatigue Inventory

Score of 20-100

Time Frame: Measured at Baseline (1 week), at completion of active stimulation, and at completion of sham stimulation

#### 10. EuroQol 5 Dimensions (EQ-5D-5L)

0-1 global index score, 0-100 VAS score of health related quality of life

Time Frame: Measured at Baseline (1 week), at completion of active stimulation, and at completion of sham stimulation

## Pre-specified Analyses

### Hypothesis testing analyses:

#### 1. Linear Mixed Effects Modelling

To explore the within-participant effect of active stimulation compared to baseline and to sham stimulation, making use of repeated measures. Testing the hypothesis that active stimulation results in greater improvement from baseline than sham stimulation.

#### 2. Within-participant comparison of clinical outcomes

Comparing change from individual baseline in active vs sham phases, using paired tests, (e.g. paired T-tests or Wilcoxon sign rank tests). Testing the hypothesis that active stimulation results in greater improvement from baseline than sham stimulation.

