#### 7. Analysis of order effect

Comparison of STIM-> SHAM vs SHAM->STIM, to explore order effect and sufficiency of 1 week washout period

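### The paired test of active against sham ignores period, so drift between the crossover periods costs power and, if the sequences are uneven, shifts the estimate

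*SAP*

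**What the plan says.** The SAP background describes the design as "Participant flow diagram; two arm crossover design", and hypothesis-generating analysis 7 names the two sequences, STIM->SHAM and SHAM->STIM.

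Two hypothesis-testing analyses address the same clinical question with the same closing sentence: "Testing the hypothesis that active stimulation results in greater improvement from baseline than sham stimulation".

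- Analysis 1 is a linear mixed model, described as "To explore the within-participant effect of active stimulation compared to baseline and to sham stimulation, making use of repeated measures". Its fixed effects are not listed.
- Analysis 2 is "Comparing change from individual baseline in active vs sham phases, using paired tests, (e.g. paired T-tests or Wilcoxon sign rank tests". It mentions neither period nor sequence.

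The SAP does not say which of the two decides the question. For the PSQI, a primary outcome, the comparison is "Within participant change, comparing active stimulation period with baseline and sham stimulation period with baseline". Table 1 schedules the PSQI once at baseline and once after each use period, so there is no second baseline before the second period.

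Order appears only in analysis 7, under the hypothesis-generating heading: "Comparison of STIM-> SHAM vs SHAM->STIM, to explore order effect and sufficiency of 1 week washout period". Nothing there says that its result adjusts the treatment estimate.

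**The concern.** A paired t-test or signed-rank test reduces each participant to one active-minus-sham difference and discards the order of the phases. Symptom scores in a crossover may change between the first and second use period for reasons unrelated to treatment, such as familiarity with the devices, regression to the mean or time itself. That change counts against active in one sequence and in its favour in the other.

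Taking change from baseline looks like protection but is not. The same baseline value is subtracted from both phases, so it drops out of their difference.

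Two things are at stake. With equal sequences, the drift is counted as error and a real effect is easier to miss. With unequal sequences, for instance after drop-out, part of the drift is also reported as treatment effect. There is a further practical risk: two tests of one hypothesis could disagree because one handles period and the other does not.

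**Working it through.** **Inputs from the SAP.** Two sequences, one baseline shared by both phases, a paired test of active against sham. The SAP states no sample size, split, SD, effect or drift, so there is no figure of its own to reproduce. Everything numerical below is an assumption chosen for illustration.

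**Notation.** tau is the extra improvement on active over sham. pi is the change in improvement from the first to the second use period. The within-participant difference has SD 1, so tau and pi are in units of that SD.

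**Step 1: the baseline cancels.** (active − baseline) − (sham − baseline) = active − sham.

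**Step 2: drift does not cancel.** The expected active-minus-sham difference is tau − pi in STIM->SHAM and tau + pi in SHAM->STIM.

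**Step 3: the paired estimate.** With n1 participants in STIM->SHAM, n2 in SHAM->STIM and N = n1 + n2:

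- Mean = tau + pi × (n2 − n1)/N. At 12/8 and pi = 0.5 the bias is 0.5 × (8 − 12)/20 = −0.10; at 8/12 it is +0.10; at 10/10 it is 0.
- The variance used by the test is about 1 + 4p(1 − p)pi², where p is the share in one sequence. At p = 0.5 and pi = 0.5 this is 1.25, so the standard error is inflated by √1.25 = 1.12. At pi = 1 the factor is √2 = 1.41.

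**Step 4: the period-adjusted estimate.** Take period 1 minus period 2 for each participant. Its expectation is tau − pi in STIM->SHAM and −tau − pi in SHAM->STIM. The difference between sequences is 2 × tau, and half of it is tau; pi is gone. The standard error is 0.5 × √(1/n1 + 1/n2) on N − 2 degrees of freedom: 0.224 at 10/10, 0.228 at 12/8 and 0.234 at 13/7.

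**Step 5: power by simulation.** N = 20, tau = 0.66, two-sided 5%, at least 40,000 simulated trials per t-test cell.

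| Split (STIM first/SHAM first) | Drift (SD) | Bias (SD) | Paired t power | Adjusted power | Paired type I error |
|---|---|---|---|---|---|
| 10/10 | 0 | 0 | 80% | 80% | 5.0% |
| 10/10 | 0.25 | 0 | 78% | 80% | 4.4% |
| 10/10 | 0.5 | 0 | 72% | 80% | 2.9% |
| 10/10 | 0.75 | 0 | 62% | 80% | 1.5% |
| 10/10 | 1.0 | 0 | 49% | 80% | 0.6% |
| 12/8 | 0.5 | −0.10 | 57% | 78% | 4.4% |
| 8/12 | 0.5 | +0.10 | 84% | 78% | 4.4% |

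The adjusted test holds 5% type I error throughout. With N = 40 and an effect of about 0.45 SD the pattern is the same: at 20/20, 78/73/50% at drifts of 0.25/0.5/1.0 SD against 80%; at 60:40 and 0.5 SD, about 50% or 89% against 78%.

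**Rank tests** (4,000 trials per cell, so about ±1.4 points). At 10/10 the signed-rank test has 76/69/42% power at drifts of 0.25/0.5/1.0 SD; the adjusted rank-sum test has about 75%. The rank form therefore gains nothing at 0.25 SD.

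**False positives.** At N = 20, type I error of the paired t-test stays at or below 5% at 10/10 and 12/8. It rises as the split becomes more uneven or the trial larger: 7.3% at 13/7 with 0.75 SD drift, 9.8% at 6/14 with 0.5 SD, and 6.2% at 24/16 with 0.5 SD. Averaged over simple randomisation at N = 20 it is 5.0%.

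**The case against.** The strongest reply is that the harm depends wholly on drift that the SAP gives no reason to expect. The periods are two weeks long and one week apart. At an equal split and 0.25 SD drift the loss is about 2 points; the 49% figure needs drift of a full SD. With equal sequences the test is unbiased and conservative, and nothing in the SAP points to an uneven split. This stands, and it is why the point is an improvement to make rather than a fatal fault.

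Second, the mixed model is listed first, tests the same hypothesis and may well include period. That is possible, but the SAP does not say so or give that model precedence. Even with period in the model, the paired test remains a stated hypothesis test. The tests are given only as examples, but both examples ignore period.

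Third, analysis 7 would reveal large drift. It could, but seeing drift afterwards does not correct a pre-specified test that left it in.

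Fourth, the adjusted form has limits. It does not remove differential carry-over, and it does not help the active-versus-baseline comparison, where baseline always comes first and is confounded with time. Both are true, and neither is a reason to leave drift in active minus sham.

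**Conclusion.** The concern holds. The algebra needs no assumption about size: in this design the named paired tests leave period drift in the differences, and the single baseline does not remove it. The main consequence is lost power: at N = 20 and 10/10, about 2 points at 0.25 SD drift, 8 at 0.5 SD and 30 at 1.0 SD. Bias of pi × (n2 − n1)/N arises only when the analysed sequences are unequal, and it can run either way. Excess false positives are not a general feature of this test; they need a clearly uneven split, or a moderately uneven one in a larger trial, together with sizeable drift.

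These sizes rest on assumed sample size, effect, split and drift. With no drift the loss is nil. The change is worth making because it is cheap, but the trial does not fail without it.

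**What to change.** - **Analysis 2.** Replace the paired test with its period-adjusted form: a two-sample t-test (or rank-sum test) of period-1 minus period-2 differences between the two sequence groups, with the difference in means halved to give the treatment effect.
- **Analysis 1.** List the fixed effects: phase (baseline, active, sham), an indicator for first or second use period, and sequence, with a random participant effect. Baseline rows can take the reference level of the period indicator. The period term removes the drift; sequence is conventional and not essential for that purpose. Say that active versus baseline remains confounded with time.
- **Precedence.** State which of analyses 1 and 2 decides the active-versus-sham hypothesis. Naming the mixed model with a period term as the main analysis, and dropping the paired test as a hypothesis test, would also meet the concern.
- **Analysis 7.** Keep it as the exploratory look at order and washout.

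The cost is SAP wording, with no new data. Statistically it is one degree of freedom. If there is no drift, t-test power is practically unchanged at 10/10 and falls from 80% to 78% at 12/8 and to 76% at 13/7; the rank-sum form loses about 2–3 points against the signed-rank test.

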#### 3. Within participant analysis of electrophysiological effect

Comparing alpha spectral power during the period of active stimulation use with the equivalent period of baseline and sham stimulation use, testing the hypothesis that hBET entrains alpha and this can be detected with DREEM headband.

#### 4. Correlation of alpha entrainment to clinical outcomes

To examine whether sleep, pain and other symptoms improve particularly in those who achieve alpha entrainment. Including: diary report of pain and sleep symptoms, symptoms reported on standardised questionnaires, actigraphy measures of sleep, DREEM headband measures of sleep.

#### 5. Adherence to the protocol

Proportion of nights correct programme used and degree of data completeness, to test whether participants can feasibly follow the protocol and use the intervention

### Hypothesis generating analyses:

#### 6. Subgroup analysis by Responder category

Response categories pre-specified as improvement with active stimulation, compared to baseline of at least 1 point on BPI pain interference score (the MCID), partial response being improvement of less than 1 point, non-response being no improvement.

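### The exploratory responder categories ignore the sham phase, so improvement that also occurs on sham is labelled response

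*SAP*

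**What the plan says.** Section 6 of the SAP (Subgroup analysis by Responder category), under "Hypothesis generating analyses", sets the top category: "Response categories pre-specified as improvement with active stimulation, compared to baseline of at least 1 point on BPI pain interference score (the MCID". The other two follow from the same change score: "partial response being improvement of less than 1 point, non-response being no improvement". The comparator is stated openly: it is baseline, and only the active phase is classified. No other section adds a sham condition. Section 6 also does not say what will be compared across the categories.

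Elsewhere the SAP sets the question against sham. Linear Mixed Effects Modelling is there "To explore the within-participant effect of active stimulation compared to baseline and to sham stimulation, making use of repeated measures". Within-participant comparison of clinical outcomes gives its aim as "Testing the hypothesis that active stimulation results in greater improvement from baseline than sham stimulation".

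The sham data needed for a controlled definition are collected. Table 1 marks the BPI as "weekly throughout", and the entry for BPI pain interference reads "Measured weekly through Baseline (1 week) active stimulation (2 weeks), washout (1 week) and sham stimulation (2 weeks".

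**The concern.** Change from baseline on active combines any effect of the device with everything else that moves the score: placebo response, regression to the mean and time. In a crossover, each participant's own sham phase is the planned control for these, and the responder rule leaves it out.

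Two cases show the effect. A participant who improves by 2 points in both phases is a full response. One who improves by 0.9 points on active and worsens on sham is only a partial response. The first shows no advantage of active over sham and the second does, yet the labels rank them the other way.

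The stake is what the analysis is for. A hypothesis-generating subgroup analysis suggests whom to study next. If the categories are read as response to stimulation, differences between them may describe people who improve in general and not people who improve because of the device.

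**Working it through.** The SAP states no responder rate, SD, sham change or correlation, so it has no figure to reproduce. The size below is illustrative, and only the 1-point threshold comes from the SAP.

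**Model.** Let A and S be improvement from baseline in BPI interference on active and on sham. Take them as bivariate normal with the same mean m (no device effect), common SD s and correlation r. Assumed values:
- m = 0, 0.5 and 1 point.
- s = 2, range 1 to 3.
- r = 0.5, range 0 to 0.8. The value 0.5 arises when both changes share one baseline score and all scores carry equal, independent errors: covariance e, variance 2e, ratio 0.5.

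**Step 1: share labelled full response by the SAP's rule.** P(A ≥ 1) = 1 − Φ((1 − m)/s). For s = 2 and m = 0.5 this is 1 − Φ(0.25) = 0.401.

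| s | m = 0 | m = 0.5 | m = 1 |
|---|---|---|---|
| 1 | 0.159 | 0.309 | 0.500 |
| 2 | 0.309 | 0.401 | 0.500 |
| 3 | 0.369 | 0.434 | 0.500 |

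The share rises with m at every SD, although the device does nothing in this model.

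**Step 2: how many of those also respond on sham.** At s = 2 and r = 0.5, P(A ≥ 1 and S ≥ 1) is 0.163, 0.240 and 0.333 for m = 0, 0.5 and 1. Dividing by step 1:
- m = 0: 0.163/0.309 = 53%.
- m = 0.5: 0.240/0.401 = 60%.
- m = 1: 0.333/0.500 = 67%.

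At s = 2 and m = 0.5, the 60% becomes 40% at r = 0 and 75% at r = 0.8. If s, m and r all vary over their ranges, it runs from about 16% (s = 1, m = 0, r = 0) to about 80% (m = 1, r = 0.8). At the central values (s = 2, m = 0.5, r = 0.5), about 30% of those labelled do no better on active than on sham.

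**Step 3: what a cross-table would show.** At the central values, the 40.1% labelled full response on active divide by sham category into 8.5% none, 7.6% partial and 24.0% full (percentages of all participants).

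**Step 4: a rule based on the difference.** A − S has mean 0 and SD s√(2(1 − r)), so P(A − S ≥ 1) = 1 − Φ(1/(s√(2(1 − r)))), which does not contain m.

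| s | r = 0 | r = 0.5 | r = 0.8 |
|---|---|---|---|
| 1 | 0.240 | 0.159 | 0.057 |
| 2 | 0.362 | 0.309 | 0.215 |
| 3 | 0.407 | 0.369 | 0.299 |

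These shares are all noise, and they can exceed those of the present rule when m is small and r is low. What the difference rule gains is that improvement common to both phases cannot raise its share. Simulation of 2,000,000 pairs at s = 2 and r = 0.5 agrees: 0.308, 0.308 and 0.309 for m = 0, 0.5 and 1, against 0.307, 0.401 and 0.500 under the present rule.

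**The case against.** The strongest reply is that the SAP says nothing false. It names baseline as the comparator, never claims that the categories identify device-specific response, and places the analysis among the exploratory ones. Harm arises only if the categories are read as response to stimulation. If active and sham outcomes were later compared within each category, sham would still enter. No primary outcome or hypothesis test depends on the categories.

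A difference-based category also has real drawbacks. It carries the noise of both phases: with no device effect and r = 0.5 it still labels 16%, 31% or 37% at SD 1, 2 or 3, the same as the present rule with no shared improvement. The SAP offers 1 point as the MCID for change from baseline and gives no support for 1 point as an active-minus-sham difference. Carryover could also distort it by sequence, and the SAP's order analysis is itself there "to explore order effect and sufficiency of 1 week washout period".

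Most of this stands, and it limits the weight of the point: the harm is conditional, the analysis is exploratory, and the difference category should be optional. It does not remove the point. Followed as written, the rule gives the name response to improvement that sham produces equally, and the data that would show this go unused in the classification. Cross-tabulating the two phases needs neither a new threshold nor a difference score.

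**Conclusion.** The concern holds. All three categories are set by the active phase alone, and improvement shared with sham is counted as response. The direction needs no assumed SD or correlation: when active and sham share the same distribution of change, a higher common mean, up to and including the threshold, raises the share labelled full response in the model used here and cannot raise a share based on the active-minus-sham difference.

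The size is not known from the SAP. Assuming normal changes, no device effect and SD 2 (range 1 to 3), the full-response share is 31% (16% to 37%) with no shared improvement, 40% (31% to 43%) with 0.5 points, and 50% at every SD with 1 point.

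The consequence is confined to this hypothesis-generating analysis. The mixed model, the paired comparisons and the alpha-power comparison all use sham and are unaffected. It should be corrected because the correction is cheap, but it does not threaten the trial's main conclusions.

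**What to change.** - Apply the same three categories to the sham phase and report the active-by-sham cross-table, overall and separately for STIM→SHAM and SHAM→STIM, because the SAP leaves the sufficiency of the washout open.
- Rename the present full-response category *improved on active*.
- Optionally, if a stimulation-specific category is wanted, base it on the active-minus-sham difference in BPI interference improvement. One point could serve as a working threshold, stated as such. Do not present it as proof of individual response.

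The cost is a change of SAP wording and one extra table, since the BPI is already collected weekly in both phases. There are three downsides to state. The difference category is noisy: about 31% would exceed 1 point by chance at SD 2 and correlation 0.5. Carryover could hide response in STIM→SHAM participants. Cells by sequence may be small.

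### Item 6 groups participants by their active-phase BPI result with no sham reference, so outcome comparisons by responder category would favour active in 'responders' even if the device did nothing

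*SAP*

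**What the plan says.** Item 6 of the SAP stands under "Hypothesis generating analyses" and is titled "Subgroup analysis by Responder category". Its top category is set by this rule: "Response categories pre-specified as improvement with active stimulation, compared to baseline of at least 1 point on BPI pain interference score (the MCID"). The other two follow: "partial response being improvement of less than 1 point, non-response being no improvement". All three depend only on the baseline score and the score under active stimulation.

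Secondary outcome 5 describes the instrument, which "gives a 0-10 score for pain interference", and its timing: "Measured weekly through Baseline (1 week) active stimulation (2 weeks), washout (1 week) and sham stimulation (2 weeks"). Each stimulation phase therefore yields two readings. Item 6 does not say whether the second week or the two-week mean is used.

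Item 6 names no outcome, contrast or test to be applied across the categories. The active-versus-sham contrast is set elsewhere. Item 1 is "Testing the hypothesis that active stimulation results in greater improvement from baseline than sham stimulation", and item 2 is "Comparing change from individual baseline in active vs sham phases, using paired tests". Neither is split by responder category.

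**The concern.** A subgroup supports a statement about who benefits only if membership is fixed before treatment. Here a participant enters the top group partly because the active-phase reading happened to be low, or the baseline reading happened to be high. Chance variation in the active reading then appears on both sides of the analysis: it decides the group, and it contributes to the result reported for the group.

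Sham readings are not selected in this way. Within 'responders' the active score is pulled down and the sham score is not; within 'non-responders' the reverse happens. What is at stake is an exploratory table showing a group with a clear device effect and a group with harm, when neither exists. Fixing the 1-point cut-off in advance does not prevent this, because the problem lies in the variable that is cut.

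**Working it through.** **Nothing to reproduce.** The SAP states no sample size, SD, correlation or expected effect for BPI interference. The 1-point threshold is a definition. The check therefore asks what item 6 would show if the device had no effect.

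**Inputs**
- From the SAP: 0-10 scale; response means baseline minus active of at least 1; non-response means no improvement; one baseline week and two weeks per stimulation phase.
- Assumed: SD s of 1.5 to 2.5 (central 2.0); correlation r between any two readings of 0.5 to 0.9 (central 0.7); common improvement m of 0, 0.5 or 1.0 point in both phases, from placebo or time; device effect zero.

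**One reading per phase.** Let B, A and S be the baseline, active and sham scores.
- Var(B−A) = 2s²(1−r), so the SD of the change is t = s√(2(1−r)).
- Cov(S−A, B−A) = s²(1−r), so the slope of S−A on B−A is s²(1−r) / 2s²(1−r) = 1/2, whatever s and r are.
- Hence E[S−A | B−A ≥ 1] = ½ · t · φ(k)/(1−Φ(k)), with k = (1−m)/t.

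Central case, m = 0: t = 2√0.6 = 1.549; k = 1/1.549 = 0.6455; φ(k) = 0.3239; 1−Φ(k) = 0.2593.
- Responders (26% of participants): ½ × 1.549 × 0.3239/0.2593 = **+0.97** point for active over sham.
- Non-responders (50%): −½ × 1.549 × 0.3989/0.5 = **−0.62**.
- Partial responders (24%): **+0.24**.
- All participants: 0. The share improving by at least 1 point under sham is also 26%.

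**Sensitivity, spurious responder advantage in points**

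| Score used | m = 0 | m = 0.5 | m = 1.0 |
|---|---|---|---|
| One reading, central case | 0.97 | 0.79 | 0.62 |
| One reading, all s and r | 0.65 to 1.34 | 0.44 to 1.16 | 0.27 to 1.00 |
| Two-week means, simulated | 0.51 to 0.94 | 0.38 to 0.77 | 0.27 to 0.61 |

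The simulated row used selected combinations with s from 1.5 to 2.5 and r from 0.5 to 0.8, scores truncated to 0-10, and weekly residual autocorrelation of 0 or 0.5.

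**Why averaging helps only in part.** With two independent weekly residuals averaged in each stimulation phase and one baseline reading, the slope falls from 1/2 to 1/3. In the central case the residual variance is 4 × 0.3 = 1.2 at baseline and 0.6 in each phase mean, so t = √1.8 = 1.342, k = 0.745, and the advantage is ⅓ × 1.342 × 0.3022/0.2280 = 0.59.

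**Lower corner.** The lower end is not a floor. With two-week means, s = 1.5, r = 0.9 and m = 1.0, the residual variance is 0.225, t = √(0.225 + 0.1125) = 0.581 and k = 0, giving ⅓ × 0.581 × 0.798 = 0.15. The bias shrinks there but keeps its sign.

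**Other outcomes.** If an outcome's occasion-to-occasion noise has correlation c with that of BPI, its bias in units of its own noise SD is c times the BPI figure in noise-SD units. With single readings and a BPI noise SD of 1.0 point the BPI figure is 0.92, so c of 0.3 to 0.5 gives 0.27 to 0.46. These are noise SDs, not between-person SDs; as a conventional standardised effect the figure would be smaller.

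**Baseline characteristics across categories.** Cov(B, B−A) is also s²(1−r), so the slope of B on B−A is again 1/2. In the central case, responders would have a baseline BPI 0.97 point above the trial mean with no device effect, which is regression to the mean. By contrast Cov(B, S−A) = 0, so relating the active-minus-sham difference to baseline is free of this artefact.

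**The case against.** The strongest reply is that the harmful analysis is inferred. Item 6 defines categories but never says that active is compared with sham inside them, and it could be read as a plan to describe the baseline profile of those who improved. It is also labelled hypothesis generating. This largely stands, and it makes the active-versus-sham bias conditional on how the categories are used. It does not clear the item: the title calls it a subgroup analysis, nothing excludes outcome comparisons, and the baseline-profile reading still lacks a sham reference.

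A reader might infer three stronger things that the document does not support.
- *That the false advantage in responders is close to the 1-point MCID.* This is right for a single reading with SD near 2, correlation near 0.7 and no common improvement. Two-week means or a shared placebo improvement bring it well below that, and the SAP gives no figures with which to choose.
- *That item 6 has a known false-positive rate.* It specifies no test and the SAP gives no sample size, so any rate would describe an analysis that is not in the plan.
- *That the trial's main conclusions are at risk.* Items 1 to 3 do not condition on responder category.

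**Conclusion.** The concern holds in conditional form. Item 6 builds its groups from an active-phase outcome without sham. If active-phase outcomes or active-minus-sham differences are compared by those groups, the result is biased towards active in 'responders' and against it in 'non-responders' under no device effect. For BPI interference the responder bias is about 0.3 to 1.3 points over the scenarios computed, and smaller with high correlation, averaging and a shared improvement together. The direction follows from the definition; the size rests wholly on assumed inputs. If only baseline characteristics are compared, the categories still cannot separate device response from placebo response and regression to the mean. The matter is minor, because the analysis is exploratory and the hypothesis-testing comparisons are unaffected, but it is worth correcting before the data are analysed.

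**What to change.** Amend item 6 to say:

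1. The responder categories are descriptive. They are not used to subgroup post-randomisation outcomes or to test active against sham.
2. Which BPI week or weeks give the active-phase score (second week or two-week mean).
3. The question of who benefits is addressed by treatment-by-baseline-characteristic interactions in the item 1 mixed model, for example with baseline pain, PSQI, HADS and baseline alpha power. A simpler alternative is to relate each participant's active-minus-sham BPI difference to those characteristics. Both remain hypothesis generating.

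If the categories are tabulated, apply the same rule to sham against baseline and show the two sets of proportions together. That gives the missing reference, but it does not make outcome comparisons within the categories valid.

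The cost is SAP wording only. The data are the same and no clinical rule changes. Outcome comparisons by responder category are dropped.
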